#### 4.3. Independent Variables

The key independent variables in this analysis are:

Study Arm – Randomized to the Intervention arm or the SOC arm.

Timing of Assessment – pre-intervention, immediately post-intervention, three-month follow-up, six-month follow-up.

#### 4.4. Covariates

As appropriate in the analyses, multivariable modeling of changes in ART adherence will include adjustment for the following participant-level characteristics:

- a. Age
- b. Sex
- c. Partner HIV status
- d. Baseline levels of adherence

#### 4.5. Statistical Analysis Methods

Descriptive statistics of key independent variables and covariates will be summarized within each arm using frequencies or means (standard deviations) as appropriate. Overall participation rates will be reported in each arm based on the proportion of baseline participants who completed the six-month follow-up assessment.

To test **hypothesis 1 (H1)**, we will conduct t-tests to assess for differences in ART adherence rates over six months (0 to 180 days) between study arms.

To test **hypothesis 2 (H2)**, we will conduct chi-square tests to assess for differences in biological measures of ART adherence between study arms. Adjustments for small sample sizes will be made as appropriate.

To test **hypothesis 3 (H3)**, we will conduct generalized linear mixed modeling to assess for change in self-reported ART adherence from baseline to the six-month follow-up period and compare between arms. Generalized linear mixed modeling will be used to account for the effect of response clustering within participants. Models will adjust for the covariates specified above (section 4.4) and include random effects for dyad and intercept.

The model testing H3 is summarized as Equation H3:

$$\begin{aligned} \text{ART adherence} = & \text{Intercept} + B_1(\text{Arm}) + B_2(\text{Categorical variable corresponding to timepoint of adherence assessment; two degrees of freedom}) + \\ & B_3(\text{Arm * Timepoint of adherence assessment; two degrees of freedom}) + B_4(\text{Baseline adherence level}) + B_5(\text{Partner HIV status}) + B_6(\text{Respondent Age}) + B_7(\text{Respondent Sex}) + \text{Error} \\ & + \text{Random effects for the clustering within participant across timepoints and by dyad.} \end{aligned}$$

If the statistical test for the interaction between arm and timepoint is significant at the  $\alpha=0.05$  level, then we conclude that study arm significantly impacts the change in ART adherence. Within arm, adjusted estimates of changes in adherence will be presented along with 95% confidence intervals.

To test **hypothesis 4 (H4)**, we will conduct chi-square tests to assess for differences in uptake of OST between study arms. Adjustments for small sample sizes will be made as appropriate.

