4.4. Inclusion/Exclusion Criteria

Participant inclusion criteria

We will recruit 66 dyads (n=132) to participate in a randomized control trial of the adapted couple-based intervention. We anticipate we will need to screen 450 individuals to obtain 66 eligible dyads (n=132). Dyads are eligible to participate if

- (1) both partners are ≥ 18 years old,
- (2) both identify each other as their intimate partner, family member, friend, or other person within their social network,

- (3) the relationship has existed at least 3 months,
- (4) both report feeling safe participating with their partner in the study,
- (5) neither reports any severe physical or sexual violence perpetrated by the other partner in the past year,
- (6) both are able to provide informed consent and follow study procedures, and
- (7) both are fluent in Russian.

In addition, the “index case” (partner initially recruited from AIDS Center) must

- (1) be confirmed HIV+ by the AIDS Center,
- (2) have been on ART at least 3 months,
- (3) not be virally suppressed according to the AIDS Center standard (<500 copies/ml), and
- (4) report injecting any drug in the past year.

“Partners” may be HIV- or HIV+ and may or may not be a PWID. Because dyad dynamics may depend on the sex of the “index case”, women will be the “index case” in at least a third of dyads. If both partners meet eligibility criteria, both will provide consent, complete the baseline assessment, and be randomized to study arm.

Participant exclusion criteria

Individuals who do not meet inclusion criteria or who meet any of the following criteria will be excluded from the study.

- (1) unable to provide informed consent,
- (2) unwilling or unable to participate in study procedures,
- (3) any condition that, in the opinion of the principal investigator and research staff, would make participation in the study unsafe, complicate interpretation of study outcome data, or otherwise interfere with achieving the study objectives.

4.5. Study Enrollment. The Baseline Visit will be conducted remotely by phone or computer with participants. At the Baseline Visit, the participants will provide informed consent, be enrolled in the study, complete the baseline assessment through Qualtrics, and self-collect urine and hair samples (if HIV-positive), which will then be mailed to the GHRCCA research staff.

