4.6.1. Baseline Visit (for all participants)

Baseline visits will be conducted remotely by phone/video call using video call platforms that are commonly used in Kazakhstan and available on participant phones or in-person in GHRCCA’s field office. Prior to remote visits, an RA will mail a baseline kit to participants containing an electronic monitoring device (EMD), study phone, and materials to self-collect hair and urine samples. The following procedures/assessments will be performed at the baseline visit:

1. The RA will complete the **Locator Information Form**;
2. The RA will send the **Baseline Assessment** through Qualtrics;
3. The RA will set-up **electronic monitoring device (EMD)** and phone app with participants. The RA will instruct the participants on proper EMD use and conduct an EMD test to confirm that the device is working properly and is connected with the data server;
4. To ensure equal distribution between study arms by the sex of the “index case” and those on tenofovir-based regimens, a randomization list will be generated. The dyad will be **randomized** to an intervention arm; If the dyad is randomized to Standard of Care, they will be sent informational materials. If they are randomized to the intervention, they will be scheduled an intervention appointment with an intervention facilitator.
5. Participants will self-collect urine samples and hair samples to measure biological levels of medication adherence. These samples will be mailed to GHRCCA staff.

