#### 3.2. Trial Randomization

#### 3.3. Data Sources

##### 3.2.1. Participant Surveys.

Participants completed surveys via Qualtrics at four timepoints -- baseline “pre-intervention”, immediately post-intervention (1-month after baseline), three-month and six-months follow-up. Among the many topics assessed, surveys included sociodemographic items, the validated self-reported three-item adherence scale, and use of OST.

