##### 3.2.2. EMD Data.

HIV-positive participants were given an EMD that continuously monitored device openings. The EMD sends a signal to a secure website via cellular data networks whenever the device is opened as a proxy for ART adherence. If connection or SIM card problems prevent real-time monitoring, records and diagnostics are stored (up to 1 year) and uploaded to the server when a connection is re-established. The device can store a 30-day supply of medication.

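### The primary EMD comparison (H1) is an unadjusted t-test with no stated analysis unit; an index-case model adjusted for baseline adherence and the two balancing factors would be modestly more precise if baseline adherence predicts EMD use

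*SAP*

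**What the plan says.** SAP 4.5 tests H1 as follows: "we will conduct t-tests to assess for differences in ART adherence rates over six months (0 to 180 days) between study arms". The dependent variable (SAP 4.2, item 1) is a count of days with a device opening, 0 to 180, starting at baseline. No covariate and no dyad term is attached to this test.

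The candidate covariates are planned data:

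- **Balancing factors.** Protocol 4.6.1 step 4 seeks equal arms by the sex of the index case and "those on tenofovir-based regimens, a randomization list will be generated". Regimen is extracted from the medical record (Protocol 4.6.9). Tenofovir regimen appears in no analysis model.
- **Baseline adherence.** SAP 3.2.1 says that "surveys included sociodemographic items, the validated self-reported three-item adherence scale", and baseline is one of its four survey timepoints. Protocol 4.4 has both partners "complete the baseline assessment, and be randomized to study arm", in that order, so the score precedes allocation.
- **Covariate list.** SAP 4.4 says that "multivariable modeling of changes in ART adherence will include adjustment for the following participant-level characteristics", and lists age, sex, partner HIV status and baseline adherence. Only the H3 model in SAP 4.5 is written with them, together with a random effect for dyad.

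On the unit of analysis, SAP 3.2.2 states that "HIV-positive participants were given an EMD that continuously monitored device openings". Protocol 4.4 says that partners "may be HIV- or HIV+ and may or may not be a PWID". SAP 4.2 counts participants per arm without limiting the count to index cases.

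**The concern.** The primary outcome gets a less efficient analysis than a secondary one, although the variables needed to improve it are collected. Protocol 4.7 wants parameters for the larger trial estimated as informatively as the pilot allows, gives 95% confidence intervals and tests the primary null hypothesis. A narrower interval serves that purpose. A t-test that leaves out factors balanced by design is also somewhat conservative if those factors are prognostic, though nothing in the documents shows that they are.

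An adjusted model cannot be written down until its unit is fixed. Dyads are randomized, and some may supply two EMD records. A t-test, or a linear model without a dyad term, that pools both members of a dyad treats correlated records as independent.

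**Working it through.** **Inputs from the documents.** Two-sided alpha 0.05 (SAP 4.1; Protocol 4.7); 33 dyads randomized per arm, 30 per arm expected for analysis (Protocol 4.6 and 4.6.12); f = .15 with 80% power from a repeated-measures ANOVA (Protocol 4.6.12); four assessments (Protocol 4.6).

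**Assumed inputs.** r, the correlation of the baseline score with EMD days; the number of HIV-positive partners with a device; the intra-dyad correlation.

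**The plan's own figure.** For the within-between interaction, lambda = f²·N·m/(1 − rho) = 0.0225 × 60 × 4 / 0.5 = 10.8, on 3 and 174 df. Power is 78.6% with rho = 0.5 (assumed) and 80.4% with rho = 0.52. The stated 80% is therefore reproducible, but it belongs to a different test from the one planned for H1.

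**The planned t-test.** Noncentral t, 30 per arm, 58 df: 80% power requires a difference of 0.736 SD.

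**The adjusted model.** Three covariates leave 55 df. Noncentrality = d·√(n/2) / √((1 − r²)·V), where V is the variance cost of chance covariate imbalance. V = 1 + 3/54 = 1.056 if all three covariates may be imbalanced (upper bound), or 1 + 1/56 = 1.018 if only the baseline score may be. The CI width ratio is √((1 − r²)·V) × t(0.975; 55)/t(0.975; 58). For example, at r = 0.3 and V = 1.056: √(0.91 × 1.056) = 0.980, times 1.001 = 0.981.

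| Assumed r | Power at 0.736 SD (V = 1.056 / 1.018) | CI width ratio |
|---|---|---|
| t-test | 80.0% | 1 |
| 0 | 77.8 / 79.2% | 1.029 / 1.010 |
| 0.2 | 79.4 / 80.8% | 1.008 / 0.990 |
| 0.3 | 81.5 / 82.9% | 0.981 / 0.964 |
| 0.4 | 84.4 / 85.7% | 0.943 / 0.926 |
| 0.5 | 88.2 / 89.3% | 0.891 / 0.875 |

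The two power curves cross at r = 0.233 / 0.139. Simulating 33 per arm balanced on both factors, with 3 per arm lost at random, gives a mean V of 1.022 and break-even at 0.151.

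**At a small effect.** Reading f = .15 as d/2 (an assumption) gives d = 0.3. The t-test has 20.8% power; the adjusted model has 19.9 / 20.5% at r = 0, 21.4 / 22.0% at r = 0.3 and 25.0 / 25.7% at r = 0.5.

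**Restricted entry.** Every index case must "not be virally suppressed according to the AIDS Center standard", which may narrow the spread of baseline adherence. If the SD falls to u = 0.7 of its unrestricted value (assumed), r′ = u·r/√(1 − r² + u²r²) turns 0.3 into 0.215 and 0.4 into 0.292.

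**Missing baseline scores.** Protocol 5.1 allows items to be refused, and SAP 4.6 does not impute. Losing one score per arm (29 analysed per arm) moves break-even to 0.298 / 0.232; losing two moves it to 0.352 / 0.298.

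**Balanced factors left out of the t-test.** Simulated type I error, index cases only, is 4.8%, 4.5% and 3.9% when the two factors explain 2%, 5% and 10% of outcome variance.

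**Two records per dyad.** This was simulated under the null with 30 dyads per arm, of which 10, 15 or 20 also contribute an HIV-positive partner, and intra-dyad correlation 0.2 / 0.4. A linear model ignoring dyads has type I error 6.1 / 7.3%, 6.5 / 8.3% and 6.5 / 8.9%. A t-test on all participants runs from about 6% to about 9%. Dyad-clustered standard errors give 5.1–5.7%; index cases only gives 4.8–5.2%.

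**The case against.** The strongest reply is that nothing here is an error. With one outcome per dyad the t-test is unbiased and holds its level. The likely gain is small: the predictor is a 30-day self-report, there is no EMD period before baseline, and entry is restricted to unsuppressed patients. At r = 0.215 power moves only to 79.7–81.1%, and at r = 0.292 to 81.3–82.7%; a single missing baseline score per arm can erase that. The 0.74 SD anchor is simply where the t-test reaches 80%; at d = 0.3 the gain at r = 0.3 is about one point. Protocol 4.7 itself names sample means, proportions and SDs as the planning parameters. The proposed covariates differ from the SAP 4.4 list. The analysis-unit question is separate and is not cured by covariates. Finally, the SAP describes randomization in the past tense and already reports scale reliability in this sample, so pre-specification may come too late.

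Most of this stands as a limit on size. It does not remove the point. The worst case for adjustment with complete covariates is about 2 points of power, and the unadjusted means and SDs that Protocol 4.7 asks for are still reported. The proposed covariates are the two factors balanced by design plus baseline adherence. Age and partner HIV status could be argued for, but each costs a further degree of freedom in about 60 people; what matters is that the set is fixed in advance. The unit has to be settled whichever model is used. The timing objection governs how the adjusted result may be labelled.

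**Conclusion.** The concern holds, as a matter of efficiency and specification rather than validity. H1 leaves out baseline adherence and both balancing factors, all of them planned data, and does not state its unit. At 0.74 SD with 30 index cases per arm, adjustment changes power by between about −2 points (r = 0) and +8 to +9 points (r = 0.5). The CI becomes 1–3% wider at r = 0, 2–4% narrower at r = 0.3 and 11–13% narrower at r = 0.5. The lower end of r is the more plausible, so a modest gain should be expected. All of this rests on an assumed r.

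The unit question does not depend on r. If partners' records were pooled, type I error of 6–9% is possible under the assumed partner counts and intra-dyad correlations. The change is worth making but is not essential; confidence is medium.

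**What to change.** Add two sentences to SAP 4.5 for H1, dated and written before EMD data are compared by arm:

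1. The analysis uses one EMD outcome per dyad, that of the index case.
2. The primary estimate is the arm difference, with 95% CI, from a linear model of EMD adherence (SAP 4.2 item 1) on arm, baseline three-item score, index-case sex and tenofovir-based regimen (yes/no).

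Keep the unadjusted means, SDs and t-test on the same index cases as supportive, and state the number analysed in each. If HIV-positive partners' EMD data are to be included, use each participant's own baseline score and add a dyad random effect or dyad-clustered standard errors. If EMD adherence has already been compared by arm, label the adjusted model supportive only.

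The cost is three degrees of freedom and no new data collection. If the covariates prove unrelated to EMD adherence, about 1–2 points of power are lost. Index cases who refused a baseline adherence item would drop out of the adjusted model because there is no imputation, so their number should be reported.

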### **3.2.3. Biological Measures.**

*Dried blood spot (DBS) samples* were collected from HIV-positive participants at their regular AIDS Center visit to assess feasibility and acceptability of the biological collection process and measure biological levels of medication. A nurse collected DBS samples by venipuncture, using a pipette to spot blood directly onto Whatman 903 ProteinSaver cards. The cards will be air-dried, individually packaged in a plastic bag with desiccant, and transferred to a -20 to -80°C freezer for storage. Only samples of participants on tenofovir-based regimens were shipped to the US.

*Hair samples.* Participants self-collected hair samples at baseline and immediately post-intervention to measure ART adherence levels. To collect hair samples, participants cut a small thatch of hair (~50 strands of hair) close to the scalp from a bottom layer of their hair. Hair was placed in a piece of tinfoil and inside a Ziploc bag labeled with their study ID. Participants shipped samples to GHRCCA staff, who then batch shipped samples to the US for testing.

*Viral load.* Participants are tested for viral load levels during every patient visit at the AIDS Center, which occurs every six months. Viral load data were abstracted from the AIDS Center electronic medical record at the closest visit prior to the baseline assessment and at the closest visit to the six-month follow-up assessment.

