#### 4.2. Dependent Variables

The dependent variables in this analysis are:

1. EMD measured ART adherence – Number of days EMD is opened from baseline to six-month follow-up (0 to 180 days) among participants in each arm.
2. Biological measures of ART adherence – Number of participants in each arm who are virally suppressed and adherent as measured through biological testing.
3. Self-reported ART adherence – Assessed by a validated three-item ART adherence scale. The three items are: 1) *Days taken* -- number of days the patient missed at least one dose of their medication (number of days, 0-30); 2) *Frequency* -- how often the patient took their medication in the way they were supposed to in the past 30 days (never/rarely/sometimes/usually/almost always/always); and 3) *Rating* – how good a job the patient did in taking their medication in the way they were supposed to in the past 30 days (very poor/poor/fair/good/very good/excellent). Responses were then linearly transformed into a scale of 0 to 100 (higher scores indicate greater adherence). The average score across the three items was calculated to represent overall adherence. Scale reliability among this sample was high (Cronbach's  $\alpha = .90$ ).
4. Uptake of OST – Number of participants who reported they were currently taking OST at the six-month follow-up.

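### The H2 comparison of viral suppression leaves unused the pre-baseline viral load that the SAP abstracts: the test is valid, but some precision and protection against chance imbalance are given up (minor)

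*SAP*

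**What the plan says.** SAP 4.5 tests the first secondary hypothesis (called H2 there) as follows: "we will conduct chi-square tests to assess for differences in biological measures of ART adherence between study arms". The only qualifier concerns small samples, not covariates. SAP 4.2 defines the outcome as "Number of participants in each arm who are virally suppressed and adherent as measured through biological testing", a binary count per arm.

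SAP 3.2.3 supplies two viral loads per participant. The first: "Viral load data were abstracted from the AIDS Center electronic medical record at the closest visit prior to the baseline assessment". The second is taken "at the closest visit to the six-month follow-up assessment". Clinic testing is routine, "which occurs every six months", so the first value may be up to about six months old at baseline.

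Protocol 4.4 requires the index case to "not be virally suppressed according to the AIDS Center standard (<500 copies/ml". Partners have no such criterion: they "may be HIV- or HIV+ and may or may not be a PWID".

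SAP 4.4 lists covariates, including baseline adherence, and says that "multivariable modeling of changes in ART adherence will include adjustment for the following participant-level characteristics". In SAP 4.5 only the self-report model (H3) uses them. Protocol 4.6.1 balances the randomisation list on index-case sex and tenofovir regimen, not on viral load.

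**The concern.** The SAP adjusts self-reported adherence for its own baseline but gives the abstracted baseline viral load no part in H2. Among index cases baseline suppression status is constant, because all must be unsuppressed at entry. The level is not constant: it can lie anywhere from 500 copies/ml upwards, and it is a natural candidate predictor of who is suppressed six months later.

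Two arms of about 30 can differ by chance in that level. An unadjusted comparison cannot separate such a difference from an intervention effect in the trial at hand. Viral load is also the only biological measure that the SAP ties to month 6: hair is collected at baseline and immediately after the intervention, and dried blood spots at a regular clinic visit. Protocol 4.7 wants the pilot's parameters estimated accurately enough to plan a larger trial, so a sharper estimate has some value.

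**Working it through.** **1. The plan's own power figure.** Protocol 4.6.12 states 80% power with 30 dyads per arm, f = 0.15 and alpha 0.05 (repeated-measures within-between ANOVA). With four occasions and an assumed correlation of 0.5, the noncentrality is 0.15² × 60 × 4 / (1 − 0.5) = 10.8. With 3 and 174 degrees of freedom the power is 0.786, which agrees with the stated figure. It does not concern viral load, for which no power is given.

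**2. The chi-square test as planned.** Assume 30 index cases per arm (33 per arm less about 10% attrition). Exact binomial calculation gives:
- null, 30% in both arms: rejection 4.9%
- 30% versus 60%: power 66.3%

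Both depend only on the marginal suppression rates, not on how prognostic the baseline value is.

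**3. Precision gained by adjustment.** Assumptions: 30 per arm; 30% versus 60% suppressed; baseline log10 viral load normal (mean 4, SD 1) truncated at 500 copies/ml. Weak, moderate and strong mean that baseline viral load predicts suppression with an AUC of about 0.59, 0.68 and 0.74. The unadjusted standard error of the risk difference is √(0.3 × 0.7/30 + 0.6 × 0.4/30) = √0.015 = 0.1225, so the 95% half-width is 1.96 × 0.1225 = 24.0 points. The adjusted half-width is 24.0 × √(variance ratio). The variance ratios and power come from simulation.

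| Baseline prognosis | Variance ratio, adjusted/unadjusted | 95% half-width, points | Power (unadjusted about 66%) |
|---|---|---|---|
| none | 1.02 | 24.2 | no real gain |
| weak | 0.99 | 23.9 | about 67% |
| moderate | 0.92 | 23.0 | about 71% |
| strong | 0.85 | 22.1 | about 76% |

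The power column flatters the adjustment. The ordinary likelihood-ratio test rejects about 5.5–6% under the null at this sample size, so part of the gain is anti-conservatism. The variance ratio is the cleaner measure.

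A second set of assumptions (control rate 27% or 50%, difference 25 points) gives ratios of 1.02 at R² = 0, 0.96–0.98 at R² about 0.05, 0.83–0.89 at 0.13–0.18 and 0.71–0.77 at 0.24–0.30.

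**4. Chance imbalance.** The between-arm difference in mean baseline has SD √(2/30) = 0.26 baseline SDs. It exceeds 0.25 SD with probability 33%, and 0.5 SD with probability 5%. Under the second set of assumptions, a 0.5 SD imbalance moves the unadjusted risk difference by 4.5–6 points at R² about 0.05, 8–11 points at 0.13–0.18 and 10–13 points at 0.24–0.30. After adjustment the shift is about zero.

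**5. Adding sex and tenofovir regimen.** If neither is prognostic, the four ratios in the table become 1.07, 1.02, 0.96 and 0.88. That is a cost of 0.03 to 0.05, and the likelihood-ratio test then rejects about 6–6.5% under the null.

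**The case against.** The strongest reply is that nothing is wrong with the chi-square test. It holds its level, and its standard error already allows for chance imbalance. A reader might infer from the imbalance figures that the planned comparison is biased or invalid. The documents do not support that: allocation is randomised, so the imbalance matters only conditionally, in a trial where it happens to occur. This part of the objection stands in full.

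The gain also rests on an input that the documents do not contain. Prognosis could be weak, since the baseline range is cut off at 500 copies/ml and the value may be about six months old. With no prognostic value, adjustment costs about 2% of variance. This stands too, and is why the result is given as a range.

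The endpoint is itself loosely defined. SAP 4.2 could be read as a composite, and it is not limited to index cases. HIV-positive partners could be counted; their baseline status can vary, and dyad clustering would then matter. The adjusted analysis must therefore name its population and cut-off.

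Finally, the SAP describes the trial in the past tense and reports a scale reliability for this sample, so an adjusted model added now could look like a choice made after seeing data. That argues for labelling it and keeping the planned test, not for leaving it out.

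Against all this, SAP 4.1 promises to study and report baseline imbalance but gives no rule for acting on it. A stated model avoids improvising one later.

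**Conclusion.** The point holds as a cheap improvement, not as an error. SAP 4.5 leaves a collected baseline value unused in H2. At 30 index cases per arm and 30% versus 60% suppressed (both assumed), using it would change the variance of the risk difference by between +2% and −15%, with about −8% at moderate prognosis. It would also remove the conditional effect of any chance imbalance in measured baseline viraemia. In interval terms the best of these cases moves the half-width from 24.0 to 22.1 points.

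It would go too far to carry this over to hair, dried blood spots, the EMD count or OST uptake. The argument concerns viral load and its own baseline only. Adjusting for baseline suppression as yes/no would achieve nothing, since that is constant among index cases.

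Severity is minor: this is one component of a secondary outcome in a pilot.

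**What to change.** Add to SAP 4.5, under H2:
- **Population and endpoint:** index cases; suppression at the clinic visit closest to the six-month assessment, below 500 copies/ml, the standard used at entry.
- **Model:** logistic regression on arm and continuous log10 viral load from the closest visit before baseline, with no other covariate. Adding index-case sex and tenofovir regimen is optional and costs about 3–5% of variance if they are not prognostic.
- **Reporting:** standardised risk difference with 95% CI, with the interval method named.
- **Test:** a Firth-penalised fit or a permutation test, not the ordinary likelihood-ratio test.
- **Alongside:** the planned chi-square test, or Fisher's test, unadjusted.
- **Label:** if the paragraph is written after data collection, say so in the SAP and in the report.

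The cost is one paragraph and one model degree of freedom. The data are already abstracted, and the entry criterion means that every index case should have a baseline value. The risk is a variance about 2% higher if that value proves uninformative.
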